#### **7.1.1. Potential Cases of Acute Kidney Injury**

Abnormal values in SCr concurrent with presence or absence of increase in BUN that meet the criteria below, in the absence of other causes of kidney injury, are considered potential cases of acute kidney injury and should be considered important medical events.

An increase of  $\geq 0.3$  mg/dL (or  $\geq 26.5$   $\mu$ mol/L) in SCr level relative to the participant's own baseline measurement should trigger another assessment of SCr as soon as practically feasible, preferably within 48 hours from awareness.

If the second assessment (after the first observations of  $\geq 0.3$  mg/dL [or  $\geq 26.5$   $\mu$ mol/L] in SCr relative to the participant's own baseline measurement) is  $\geq 0.4$  mg/dL (or  $\geq 35.4$   $\mu$ mol/L), the participant should be discontinued from the study and adequate, immediate, supportive measures taken to correct apparent acute kidney injury.

Participants should return to the investigator site and be evaluated as soon as possible, preferably within 48 hours from awareness of the second assessment confirming abnormal SCr result. This evaluation should include laboratory tests, detailed history, and physical assessment. In addition to repeating SCr, laboratory tests should include serum BUN, serum creatine kinase, and serum electrolytes (including at a minimum potassium, sodium, phosphate/phosphorus, and calcium), in addition to urinary dipstick, urine microscopic examination, and urinary indices. All cases confirmed on repeat testing as meeting the

laboratory criteria for acute kidney injury, with no other cause(s) of laboratory abnormalities identified, should be considered potential cases of drug-induced kidney injury irrespective of availability of all the results of the investigations performed to determine etiology of the abnormal SCr. If  $\geq 2$  healthy participants are noted to have 2 consecutive SCr results of  $\geq 0.3$  mg/dL (or  $\geq 26.5$   $\mu$ mol/L), an assessment of whether the finding may be considered an adverse drug reaction should be undertaken.

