### 1.3. Schedule of Activities

The SoA table provides an overview of the protocol visits and procedures. Refer to the **STUDY ASSESSMENTS AND PROCEDURES** section of the protocol for detailed information on each procedure and assessment required for compliance with the protocol.

The investigator may schedule visits (unplanned visits) in addition to those listed in the SoA table, in order to conduct evaluations or assessments required to protect the well-being of the participant.

Visit Identifier Abbreviations used in this table may be found in Appendix 8	Screening a	Periods 1-2 b													28-35 days (Follow-Up)	Early Termination/Discontinuation	
		Day -1	Day 1														
Days Relative to Day 1	Days -28 to -2	0	0.5	1	1.5	2	2.5	3	4	6	8	12	16	24	48		
Hours After Dose																	
Informed consent	X																
CRU Confinement c		X	→	→	→	→	→	→	→	→	→	→	→	→	X		
Inclusion/exclusion criteria	X	X u															
Medical/medication history (update) d	X	X u															
Demography e	X																
Physical exam f	X	X u															
Safety laboratory (including aPTT, PT-INR, Fibrinogen, and eGFR) g	X	X u												X		X	
FSH h	X																
Urine drug testing i	X	X u															
Serology: HBsAg, HBsAb, HBcAb, HCVAb, and HIV j	X																
Pregnancy test (WOCBP only)	X	X u												X		X	
Contraception check k	X	X u													X		
Single supine 12-lead ECG l	X		X v											X		X	
Vital signs (BP/PR/RR/temperature) m	X		X v											X		X	
COVID-19 questionnaire n	X	X u															

PFIZER CONFIDENTIAL

Visit Identifier Abbreviations used in this table may be found in Appendix 8	Screening a	Periods 1-2 b													28-35 days (Follow-Up)	Early Termination/Discontinuation	
		Day -1	Day 1														
Days Relative to Day 1	Days -28 to -2	0	0.5	1	1.5	2	2.5	3	4	6	8	12	16	24	48		
Hours After Dose																	
COVID-19 testing o	X	X u															
Ritonavir administration b		X										X					
PF-07321332/ritonavir administration q			X														
PK Blood Sampling for PF-07321332 r			X	X	X	X	X	X	X	X	X	X	X	X	X	X	X
CCI																	

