Serious and nonserious AE monitoring	X	→	→	→	→	→	→	→	→	→	→	→	→	→	→	X	X
Concomitant treatments			X	→	→	→	→	→	→	→	→	→	→	→	→	X	X
CRU discharge t																X	

- a. Screening will be performed within 28 days prior to the first dose of PF-07321332/ritonavir.
- b. Period 2 will begin on Study Period1, Day 4 (referred to as Period 2, Day -1).
- c. Participants will be admitted to the CRU at least -12 hours prior to PF-07321332 dose on Day 1. Participants will be discharged on Day 3 of Period 2 following the final assessments.
- d. Medical history will include a history of prior illegal drug, alcohol, and tobacco use, as well as blood donation within prior 60 days. Medical history will be recorded at screening and updated on Day -1 of Period 1.
- e. Demographics will include participant race, ethnicity, age, and gender during the screening visit.
- f. Physical exam will be performed by trained medical personnel at the investigator site at screening or Day -1 of Period 1 only (height and weight must be obtained at screening to obtain BMI for eligibility criteria). A targeted PE may be performed at other designated time points at the discretion of the investigator.
- g. Safety laboratory assessments including urinalysis, hematology, chemistry and coagulation will be performed at the indicated time-points. All the safety laboratory samples must be collected following at least a 4-hour fast. Additional safety laboratory assessments may be performed at any time at the discretion of the investigator.
- h. For postmenopausal (amenorrheic for at least 12 consecutive months) female participants only.
- i. Urine drug (mandatory) and alcohol breath test (at discretion of investigator) will be performed at screening and on Day -1. These tests may be performed at any other time at the discretion of the investigator.
- j. HBsAb will be tested if HBsAg and/or HBcAb are positive.
- k. The investigator or his/her designee will discuss with the participant the need to use highly effective contraception consistently and correctly according to contraception guidelines.
- l. All ECG assessments will be made after at least a 5 minute rest in a supine position and prior to any blood draws or vital sign measurements. Day 3 ECG for Period 2 only.

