- m. Single supine BP, RR and PR will be performed following at least a 5 minute rest in a supine position. BP, RR and PR assessments will be performed after collection of ECGs and prior to collection of blood draws if scheduled at the same time. Day 3 measurements are for Period 2 only. Temperature will be measured as per CRU standard practice.

PFIZER CONFIDENTIAL

Visit Identifier Abbreviations used in this table may be found in Appendix 8	Screening a	Periods 1-2 b												28-35 days (Follow-Up)	Early Termination/Discontinuation			
Days Relative to Day 1	Days -28 to -2	Day -1	Day 1										Day 2	Day 3	Day 28-35 w			
Hours After Dose			0	0.5	1	1.5	2	2.5	3	4	6	8	12	16	24	48		

n. Check exposure to positive participant, residence or travel in area of high incidence and COVID-19 related signs and symptoms.

o. The testing for COVID-19 pathogen by RT-PCR will be performed at each visit. For participants admitted for residence, a subsequent COVID-19 test will be performed after 4 days (ie, upon completion of 4 x 24 hours in house), or if they develop COVID-19 like symptoms.

p. Ritonavir will be administered orally -12 hours and 12 hours relative to PF-07321332/ritonavir dosing on Day 1.

q. PF-07321332/ritonavir will be administered orally after overnight fasting on Day 1 of each treatment period.

r. One (approximately 4 mL) blood sample for PK analysis of PF-07321332 will be taken at the designated time points post dose in each dosing period.

t. Participants will be discharged after collection of the 48-hour PK sample of period-2 dosing.

u. Period 1 only.

v. Collected at pre-dose for Period 1 only.

w. Contact may occur via telephone and must occur 28 to 35 days from administration of the final dose of study intervention.

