**Table 3. Protocol-Required Safety Laboratory Assessments**

Hematology	Chemistry	Urinalysis	Other
Hemoglobin	BUN and creatinine	Local Dipstick:	

• SARS-CoV-2 RT-PCR

Hematocrit	Glucose (fasting)	pH	

• Urine drug screeningc

RBC count	Calcium	Glucose (qual)	

• Pregnancy test (<math>\beta</math>-hCG)d

MCV	Sodium	Protein (qual)	

• eGFR [CKD-EPI]

MCH	Potassium	Blood (qual)	
MCHC	Chloride	Ketones	Coagulation:
Platelet count	Total CO 2 (bicarbonate)	Nitrites	

• aPTT

WBC count	AST, ALT	Leukocyte esterase	

• PT-INR

Total neutrophils (Abs)	Total bilirubin	Laboratory:	

• Fibrinogen

Eosinophils (Abs)	Alkaline phosphatase	Microscopy and	At screening only:
Monocytes (Abs)	Uric acid	Culture a	

• FSHb

Basophils (Abs)	Albumin		

• HBsAg

Lymphocytes (Abs)	Total protein		

• HBsAbe

			

• HBcAb

			

• HCVAb

			

• HIV

- Only if urine dipstick is positive for blood, protein, nitrites, or leukocyte esterase and culture only if bacteriuria.
- For confirmation of postmenopausal status only.
- The minimum requirement for drug screening includes cocaine, THC, opiates/opioids, benzodiazepines, and amphetamines (others are site and study specific).
- Local urine testing will be standard for the protocol unless serum testing is required by local regulation or IRB/EC. Serum  $\beta$ -hCG for female participants of childbearing potential.
- HBsAb will be tested if HBsAg and/or HBcAb are positive.

The investigator must review the laboratory report, document this review, and record any clinically relevant changes occurring during the study in the AE section of the CRF.

Any remaining serum/plasma from samples collected for clinical safety laboratory measurements at baseline and at all times after dose administration may be retained and stored for the duration of the study. **CCI**

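### Protocol 7.1.1 words two serum creatinine limits, for discontinuation and for study-level review, as absolute values although rises from baseline are evidently meant

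*Protocol*

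**What the plan says.** Protocol 7.1.1 (Potential Cases of Acute Kidney Injury) acts on SCr at three levels.

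- **Repeat test.** A rise of at least 0.3 mg/dL (26.5 µmol/L) over the participant's "own baseline measurement should trigger another assessment of SCr".
- **Discontinuation.** If the second assessment is at least 0.4 mg/dL (35.4 µmol/L), "the participant should be discontinued from the study and adequate, immediate, supportive measures taken to correct apparent acute kidney injury". A baseline is mentioned in this sentence, but inside a bracket that describes the first observation. The main clause compares the second value itself with 0.4 mg/dL.
- **Study-level review.** If two or more "healthy participants are noted to have 2 consecutive SCr results of" at least 0.3 mg/dL (26.5 µmol/L), then "an assessment of whether the finding may be considered an adverse drug reaction should be undertaken". This sentence mentions neither an increase nor a baseline.

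No other section restates the second or third limit as a rise. Creatinine belongs to the routine safety chemistry ("BUN and creatinine" in Appendix 2, Table 3), so these limits apply to results that every participant will have.

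**The concern.** Protocol 2.3.1 lists renal toxicity among the potential risks of ritonavir and relies on observation of renal function to mitigate it. Section 7.1.1 is the only numeric renal rule in the protocol. The list of discontinuation reasons in 7.1 gives no creatinine limit.

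Taken at its word, the discontinuation limit cannot tell a confirmed rise from a full return to baseline. The study-level limit counts results that would be unremarkable in a healthy adult. A healthy participant could be withdrawn although the repeat test was reassuring, in a study of about 12 people, and an adverse-drug-reaction assessment could be called for with nothing to assess.

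The protocol words comparable rules clearly elsewhere. The QTcF rule in 8.2.3 and the bilirubin rule for participants with raised baseline values in Appendix 6 both state a change from baseline.

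**Working it through.** **Inputs.** The limits of 0.3 and 0.4 mg/dL, with their µmol/L equivalents, come from Protocol 7.1.1. The documents give no baseline SCr, so baseline *b* is assumed to be 0.5, 0.8 or 1.1 mg/dL.

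**Are the printed figures themselves sound?** 26.5 / 0.3 = 88.3 and 35.4 / 0.4 = 88.5, so both pairs agree with one conversion factor of about 88.4 µmol/L per mg/dL. The numbers are not misprinted. The problem lies in what they are compared with.

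**Written against intended limits.** The intended discontinuation limit is *b* + 0.4 and the intended study-level limit is *b* + 0.3. As written they are 0.4 and 0.3, so the gap is *b* in each case.

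| Assumed baseline *b* (mg/dL) | Value that prompts a repeat, *b* + 0.3 | Discontinuation: intended / written | Study-level: intended / written | Repeat needed to avoid discontinuation, as written |
|---|---|---|---|---|
| 0.5 | 0.8 | 0.9 / 0.4 | 0.8 / 0.3 | below 0.4, more than 0.1 under baseline |
| 0.8 | 1.1 | 1.2 / 0.4 | 1.1 / 0.3 | below 0.4, more than 0.4 under baseline |
| 1.1 | 1.4 | 1.5 / 0.4 | 1.4 / 0.3 | below 0.4, more than 0.7 under baseline |

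**Discontinuation limit.** A repeat exactly back at baseline equals *b*, so it meets the written limit whenever *b* ≥ 0.4. To avoid discontinuation, the repeat must fall from *b* + 0.3 to below 0.4. That is a drop of more than 0.4/0.8 = 50.0%, 0.7/1.1 = 63.6% or 1.0/1.4 = 71.4% at the three baselines. Also, *b* + 0.3 exceeds 0.4 for any *b* above 0.1, so the value that prompts the repeat already lies above the limit that the repeat is meant to test.

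**Study-level limit.** Each assumed baseline exceeds 0.3 mg/dL, so two consecutive unchanged results meet it.

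**Direction of the error.** For any *b* > 0, 0.4 < *b* + 0.4 and 0.3 < *b* + 0.3. Every value that meets an intended limit therefore meets the written one too. The wording can trigger too often but cannot miss a rise.

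**The case against.** The strongest reply is that the section explains itself. Its first limit defines a rise from baseline. The bracket in the next sentence refers back to that first observation without repeating the word increase, so a bare figure in mg/dL can be read as shorthand for a rise. The section opens by speaking of abnormal values, describes the second assessment as confirming an abnormal result, and places the study-level sentence straight after cases confirmed on repeat testing. No investigator is likely to treat a normal creatinine as kidney injury. The study-level limit leads only to an assessment. Protocol 8 (safety issues discussed with the sponsor) and 8.2.4 (repeat testing of clinically significant abnormal values) add judgement-based safeguards.

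Most of this stands, and it settles the intent and the low severity. It does not correct the thresholds. The shorthand argument is weakest for the study-level sentence, which has no baseline wording at all, and a discontinuation rule should not depend on the reader silently amending it.

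Three stronger readings are tempting but not supported:

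- **The study-level limit is met by everyone before dosing**, because safety chemistry is scheduled at screening and on Day -1 of Period 1. The sentence follows confirmed cases and asks about an adverse drug reaction, which presupposes exposure. Counting pre-dose results is contrived.
- **The rule is unable to signal renal toxicity.** The error is towards over-triggering, so a true rise would still trigger it.
- **The SCr baseline is undefined, as a separate error.** SAP 3.5.2 defines the laboratory baseline as the last measurement before PF-07321332 in Period 1. Protocol 7.1.1 does not repeat this, but that is a matter of convenience.

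**Conclusion.** The concern holds as a wording error in two decision thresholds, and it is minor. As written, both limits lie below the intended ones by the participant's whole baseline, which is 0.5 to 1.1 mg/dL over the assumed range. The conclusion on discontinuation does not depend on that range: it needs only a baseline of 0.4 mg/dL or more. For the study-level limit, any ordinary value of 0.3 mg/dL or more counts.

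The practical effect is small, because a site would probably apply the intended meaning and the error is on the cautious side. The PK analysis method is unaffected. The worst realistic outcome is an unnecessary withdrawal or an unnecessary review.

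**What to change.** In Protocol 7.1.1, change two phrases:

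- Discontinuation: *the second assessment shows an increase over the participant's baseline of ≥0.4 mg/dL (≥35.4 µmol/L)*.
- Study-level review: *2 consecutive post-dose SCr results, each showing an increase over the participant's baseline of ≥0.3 mg/dL (≥26.5 µmol/L)*.

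As an optional clarification, cite the SAP 3.5.2 baseline in 7.1.1, so that site staff need not look for it in an analysis document. The grading of 0.3 mg/dL for review and 0.4 mg/dL for discontinuation can stay.

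The cost is two phrases and, if wanted, one cross-reference. No tests are added and no analysis changes.

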## **7.2. Participant Discontinuation/Withdrawal From the Study**

A participant may withdraw from the study at any time at his/her own request. Reasons for discontinuation from the study include the following:

- Refused further study procedures;
- Lost to follow-up;
- Death;
- Study terminated by sponsor;
- Investigator's decision;
- Pregnancy

At the time of discontinuing from the study, if possible, an early discontinuation visit should be conducted. See the [SoA](#) for assessments to be collected at the time of study discontinuation and follow-up and for any further evaluations that need to be completed.

The early discontinuation visit applies only to participants who are enrolled/randomized and then are prematurely withdrawn from the study. Participants should be questioned regarding their reason for withdrawal.

The participant will be permanently discontinued from the study intervention and the study at that time.

If a participant withdraws from the study, he/she may request destruction of any remaining samples taken and not tested, and the investigator must document any such requests in the site study records and notify the sponsor accordingly.

If the participant withdraws from the study and also withdraws consent (see Section 7.2.1) for disclosure of future information, no further evaluations should be performed and no additional data should be collected. The sponsor may retain and continue to use any data collected before such withdrawal of consent.

### **7.2.1. Withdrawal of Consent**

Participants who request to discontinue receipt of study intervention will remain in the study and must continue to be followed for protocol-specified follow-up procedures. The only

exception to this is when a participant specifically withdraws consent for any further contact with him or her or persons previously authorized by the participant to provide this information. Participants should notify the investigator in writing of the decision to withdraw consent from future follow-up, whenever possible. The withdrawal of consent should be explained in detail in the medical records by the investigator, as to whether the withdrawal is only from further receipt of study intervention or also from study procedures and/or posttreatment study follow-up, and entered on the appropriate CRF page. In the event that vital status (whether the participant is alive or dead) is being measured, publicly available information should be used to determine vital status only as appropriately directed in accordance with local law.

### **7.3. Lost to Follow up**

A participant will be considered lost to follow-up if he or she repeatedly fails to return for scheduled visits and is unable to be contacted by the study site.

The following actions must be taken if a participant fails to attend a required study visit:

- The site must attempt to contact the participant and reschedule the missed visit as soon as possible. Counsel the participant on the importance of maintaining the assigned visit schedule and ascertain whether the participant wishes to and/or should continue in the study;
- Before a participant is deemed lost to follow-up, the investigator or designee must make every effort to regain contact with the participant (where possible, 3 telephone calls and, if necessary, a certified letter to the participant's last known mailing address or local equivalent methods). These contact attempts should be documented in the participant's medical record;
- Should the participant continue to be unreachable, he/she will be considered to have withdrawn from the study.

## **8. STUDY ASSESSMENTS AND PROCEDURES**

The investigator (or an appropriate delegate at the investigator site) must obtain a signed and dated ICD before performing any study-specific procedures.

Study procedures and their timing are summarized in the [SoA](#). Protocol waivers or exemptions are not allowed.

Safety issues should be discussed with the sponsor immediately upon occurrence or awareness to determine whether the participant should continue or discontinue study intervention.

Adherence to the study design requirements, including those specified in the [SoA](#), is essential and required for study conduct.

All screening evaluations must be completed and reviewed to confirm that potential participants meet all eligibility criteria. The investigator will maintain a screening log to record details of all participants screened and to confirm eligibility or record reasons for screening failure, as applicable.

Participants will be screened within 28 days prior to administration of the study intervention to confirm that they meet the study population criteria for the study. If the time between screening and dosing exceeds 28 days as a result of unexpected delays (eg, delayed drug shipment), then participants do not require rescreening if the laboratory results obtained prior to first dose administration meet eligibility criteria.

Every effort should be made to ensure that protocol-required tests and procedures are completed as described. However, it is anticipated that from time to time there may be circumstances outside the control of the investigator that may make it unfeasible to perform the test. In these cases, the investigator must take all steps necessary to ensure the safety and well-being of the participant. When a protocol-required test cannot be performed, the investigator will document the reason for the missed test and any corrective and preventive actions that he or she has taken to ensure that required processes are adhered to as soon as possible. The study team must be informed of these incidents in a timely manner.

If an IV catheter is utilized for blood sample collections, ECGs and vital sign assessments (pulse rate and BP) should be collected prior to the insertion of the catheter.

For samples being collected and shipped, detailed collection, processing, storage, and shipment instructions and contact information will be provided to the investigator site prior to initiation of the study.

The total blood sampling volume for individual participants in this study is approximately 160 mL. The actual collection times of blood sampling may change. Additional blood samples may be taken for safety assessments at times specified by Pfizer, provided the total volume taken during the study does not exceed 550 mL during any period of 56 consecutive days.

To prepare for study participation, participants will be instructed on the information in the Protocol [Section 5.3](#) Lifestyle Considerations and [Section 6.8](#) Concomitant Therapy.

